3.6. Optional Archival Sample

PPD [Redacted]

[Redacted]

4. SUBJECT POPULATION

4.1. Number of Subjects and Subject Selection

Approximately 50 subjects will be enrolled. In order to manage the total study enrollment, Gilead Sciences, Inc., at its sole discretion, may suspend screening and/or enrollment at any site or study-wide at any time.

4.2. Inclusion Criteria

Subjects must meet all of the following inclusion criteria to be eligible for participation in this study.

- 1) Willing and able to provide written informed consent
- 2) Male or female, age ≥ 18 years
- 3) HCV RNA \geq LLOQ at Screening
- 4) Received SOF/VEL/VOX for 8 weeks or SOF/VEL for 12 weeks in GS-US-367-1172 (POLARIS-2), GS-US-367-1173 (POLARIS-3), or GS-US-367-1170 (POLARIS-4), or received HCV treatment with a DAA-based regimen in another Gilead-sponsored study, with approval from Gilead Sciences prior to Screening

The subject must have completed the protocol-mandated treatment and posttreatment assessments in the prior Gilead-sponsored study.

- 5) Cirrhosis Determination
 - a) Presence of cirrhosis is defined as any one of the following:
 - i) FibroTest[®] score > 0.75 and AST:platelet ratio index (APRI) > 2 during Screening
 - ii) Liver biopsy showing cirrhosis (e.g., Metavir score = 4 or Ishak score ≥ 5)
 - iii) Transient elastography (FibroScan[®]) with a result of > 12.5 kPa
 - b) Absence of cirrhosis is defined as any one of the following, unless the definition of cirrhosis has been met:
 - i) FibroTest[®] score ≤ 0.48 and APRI ≤ 1 performed during Screening
 - ii) Liver biopsy within 2 years of Screening showing absence of cirrhosis
 - iii) Transient elastography (FibroScan[®]) with a result of ≤ 12.5 kPa within 6 months of Day 1

- 6) Liver imaging within 6 months prior to Day 1 is required in cirrhotic subjects to exclude hepatocellular carcinoma (HCC)
- 7) Females of childbearing potential (as defined in [Appendix 4](#)) must have a negative serum pregnancy test at Screening and a negative urine pregnancy test on Day 1 prior to enrollment
- 8) Male subjects and female subjects of childbearing potential who engage in heterosexual intercourse must agree to use protocol specified method(s) of contraception as described in [Appendix 4](#)
- 9) Lactating females must agree to discontinue nursing before starting study drug.
- 10) Subject must be of generally good health, with the exception of chronic HCV infection, as determined by the investigator
- 11) Subject must be able to comply with the dosing instructions for study drug administration and able to complete the study schedule of assessments

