- To evaluate the kinetics of circulating HCV RNA during treatment and after cessation of treatment
- To evaluate the emergence of viral resistance to SOF, VEL, and VOX during treatment and after cessation of treatment

Study Design:	
Approximately 50 subjects with chronic HCV infection who did not achieve an SVR in a prior Gilead-sponsored HCV treatment study will be enrolled.
 
Subjects will receive SOF/VEL/VOX FDC (400/100/100 mg) once daily with food for 12 weeks.

Number of Subjects Planned:	Approximately 50 subjects.
Target Population:	Adults with chronic hepatitis C virus (HCV) infection who participated in a prior Gilead-sponsored HCV treatment study and did not achieve SVR
Duration of Treatment:	Subjects will be treated for 12 weeks.
Diagnosis and Main Eligibility Criteria:	
Chronically HCV-infected male and non-pregnant/non-lactating female subjects aged 18 years or older who did not achieve SVR in a prior Gilead-sponsored HCV treatment study.
 
Refer to Section 4.2 and 4.3 for detailed Inclusion and Exclusion Criteria.

Study Procedures/ Frequency:	
All subjects will complete the following study visits: Screening, Day 1, and on-treatment visits at the end of Weeks 2, 4, 8, and 12. Posttreatment visits will occur at Weeks 4 and 12 after last dose of study drug.
 
Screening assessments will include physical examination, medical history, height, weight, vital signs, 12-lead electrocardiogram (ECG), adverse events related to Screening procedures, concomitant medications, safety laboratory tests (including hematology, chemistry, and coagulation), HCV RNA, HCV genotyping, serology (HCV, HBV, HIV), hemoglobin A1c (HbA1c), assessment of the presence or absence of cirrhosis (including Fibrotest[®]), screening for hepatocellular carcinoma (HCC) for subjects with cirrhosis, serum β-human chorionic gonadotropin (β-hCG) (females of child-bearing potential only), IL28B genotyping, urinalysis, and urine drug screen.
 
On-treatment assessments include adverse events (AEs), concomitant medications, study drug dispensation and pill count, physical examination, weight, vital signs, safety laboratory tests, HCV RNA, pharmacokinetic samples (after Day 1), and urine pregnancy tests (females of childbearing potential only). Samples for the viral RNA sequencing/phenotyping will be collected at Day 1 and every visit thereafter. Single 12-lead ECGs will be collected at Early Termination (ET), if applicable.

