1.3. Rationale for This Study

The population of this study will be subjects with chronic HCV infection who have previously not achieved SVR following treatment in a Gilead-sponsored trial. The majority of subjects will have received SOF/VEL for 12 weeks, or SOF/VEL/VOX FDC for less than 12 weeks. At this time there are no approved retreatment options for these patients. With the increasing use of NS5A inhibitors with or without NS5B inhibitors, the unmet medical need for effective retreatment options for the few patients who fail these regimens will increase. This study will help inform the role of SOF/VEL/VOX FDC for 12 weeks for these patients.

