4.3. Exclusion Criteria

Subjects who meet *any* of the following exclusion criteria are not to be enrolled in this study.

- 12) Current or prior history of any of the following:
 - a) Clinically significant illness (other than HCV) or any other major medical disorder that may interfere with subject treatment, assessment or compliance with the protocol; subjects currently under evaluation for a potentially clinically significant illness (other than HCV) are also excluded
 - b) Gastrointestinal disorder or post-operative condition that could interfere with the absorption of the study drug
 - c) Difficulty with blood collection and/or poor venous access for the purposes of phlebotomy
 - d) Hepatic decompensation (e.g., clinical ascites, encephalopathy, and/or variceal hemorrhage)
 - e) Solid organ transplantation
 - f) Significant cardiac disease
 - g) Unstable psychiatric condition including hospitalization, suicide attempt, and/or a period of disability as a result of their psychiatric illness within 2 years prior to Screening

- h) Malignancy within the 5 years prior to Screening, with the exception of specific cancers that have been cured by surgical resection (e.g., basal cell skin cancer, etc.). Subjects under evaluation for possible malignancy are not eligible
 - i) Significant drug allergy (e.g., hepatotoxicity)
- 13) Screening ECG with clinically significant abnormalities
- 14) Subject has the following laboratory parameters at Screening:
- a) $ALT > 10 \times$ the upper limit of normal (ULN)
 - b) $AST > 10 \times$ ULN
 - c) Direct bilirubin $> 1.5 \times$ ULN
 - d) Platelets $< 50,000/\mu\text{L}$
 - e) $HbA1c > 8.5\%$
 - f) Creatinine clearance (Cr_{cl}) < 50 mL/min as calculated by the Cockcroft-Gault equation {Cockcroft 1976}
 - g) Hemoglobin < 10 g/dL
 - h) Albumin < 3 g/dL
 - i) International Normalized Ratio of prothrombin time (INR) $> 1.5 \times$ ULN unless subject has known hemophilia or is stable on an anticoagulant regimen affecting INR
- 15) Prior treatment with SOF/VEL/VOX±RBV for ≥ 12 weeks
- 16) Chronic liver disease of a non-HCV etiology (e.g., hemochromatosis, Wilson's disease, alfa-1 antitrypsin deficiency, cholangitis)
- 17) Infection with human immunodeficiency virus (HIV)
- 18) Hepatitis B surface antigen positive (HBsAg+) at Screening

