7.2.2. Assessment of Severity

The severity grading of AEs will be assessed as Grade 1, 2, 3, or 4 using the GSI Grading Scale for Severity of Adverse Events and Laboratory Abnormalities ([Appendix 3](#)). For AEs associated with laboratory abnormalities, the event should be graded on the basis of the clinical severity in the context of the underlying conditions; this may or may not be in agreement with the grading of the laboratory abnormality.

7.3. Investigator Requirements and Instructions for Reporting Adverse Events and Serious Adverse Events to Gilead

Requirements for collection prior to study drug initiation:

After informed consent, but prior to initiation of study medication, the following types of events should be reported on the eCRF: all SAEs and AEs related to protocol-mandated procedures.

A subject's treatment history is a pre-requisite for entry into the study (eg, lack of effect of a prior Gilead product for the treatment of HCV); this will not be recorded on a Special Situations Report (SSR).

Adverse Events:

Following initiation of study drug, collect all AEs, regardless of cause or relationship, special situation reports, and pregnancy reports until 30 days after last dose of study drug.

All AEs should be followed up until resolution or until the AE is stable, if possible. Gilead Sciences may request that certain AEs be followed beyond the protocol defined follow-up period.

Serious Adverse Events:

All SAEs, regardless of cause or relationship, that occurs after the subject first consents to participate in the study (i.e., signing the informed consent) and throughout the duration of the study, including the protocol-required posttreatment follow-up period, must be reported to the eCRF database and Gilead Drug Safety and Public Health (DSPH) as instructed. This also includes any SAEs resulting from protocol-associated procedures performed after informed consent is signed.

Investigators are not obligated to actively seek SAEs after the protocol defined follow up period however, if the investigator learns of any SAEs that occur after study participation has concluded and the event is deemed relevant to the use of study drug, he/she should promptly document and report the event to Gilead DSPH.

All AEs and SAEs will be recorded in the eCRF database within the timelines outlined in the eCRF completion guideline.

Electronic Serious Adverse Event (eSAE) Reporting Process

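### Do the numbered eligibility criteria let in subjects whose earlier treatment had succeeded?

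*Protocol*

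**What the plan says.** The numbered criteria bear on earlier treatment in four places.

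- Criterion 4, first sentence: "Received SOF/VEL/VOX for 8 weeks or SOF/VEL for 12 weeks in GS-US-367-1172 (POLARIS-2", continuing to POLARIS-3 and POLARIS-4, or a DAA-based regimen in another of the sponsor's studies with approval before Screening.
- Criterion 4, second sentence: "The subject must have completed the protocol-mandated treatment and posttreatment assessments in the prior Gilead-sponsored study".
- Criterion 3: "HCV RNA \geq LLOQ at Screening".
- Exclusion 15: "Prior treatment with SOF/VEL/VOX±RBV for ≥ 12 weeks".

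None of these states the outcome of the earlier treatment. Other parts of the protocol do.

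- The Synopsis gives the outcome condition in three rows: Study Design, Target Population, and Diagnosis and Main Eligibility Criteria. The last limits entry to subjects "who did not achieve SVR in a prior Gilead-sponsored HCV treatment study", then adds "Refer to Section 4.2 and 4.3 for detailed Inclusion and Exclusion Criteria".
- Section 1.3 describes the population as subjects "who have previously not achieved SVR following treatment in a Gilead-sponsored trial".
- Section 7.3, in a rule on safety reporting, says that "treatment history is a pre-requisite for entry into the study (eg, lack of effect of a prior Gilead product".
- Protocol 8.7 and SAP 1.3 base the sample size on eligible subjects who did not reach SVR12 in the sponsor's earlier studies.

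Protocol 1.3.1 and 3.1 and SAP 1.2 mention earlier treatment without its outcome. They are less specific and do not contradict the rest.

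**The concern.** The study has one arm, and its primary result is one proportion, SVR12 in the Full Analysis Set, which counts every enrolled subject who took a dose. That proportion is meant to describe retreatment after failure. A subject who reached SVR12 earlier and became viraemic again, by reinfection or late relapse, satisfies criteria 3 and 4 as worded and would count in it. SAP 3.4 and 5.2 classify subjects by earlier regimen and not by earlier outcome, so the planned summaries would not separate such a subject. The Synopsis and Section 1.3 also write SVR with no timepoint, while the sample-size text writes SVR12, which seems to leave the status of a late relapser open.

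**Working it through.** **1. Size of the group that criterion 4's named route covers.** Arm sizes and SVR12 rates come from Protocol 1.2.2.4. The number without SVR12 is n - round(n × rate).

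| Study and arm | n | SVR12 | Without SVR12 |
|---|---|---|---|
| POLARIS-2, SOF/VEL/VOX 8 weeks | 501 | 95.0% | 25 |
| POLARIS-2, SOF/VEL 12 weeks | 440 | 98.2% | 8 |
| POLARIS-3, SOF/VEL/VOX 8 weeks | 110 | 96.4% | 4 |
| POLARIS-3, SOF/VEL 12 weeks | 109 | 96.3% | 4 |
| POLARIS-4, SOF/VEL 12 weeks | 151 | 90.1% | 15 |
| Total | 1311 | | 56 |

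Responders: 1311 - 56 = 1255, and 1255/56 = 22.4 per non-responder. The regimen clause is therefore broad, and among the numbered criteria it is criterion 3 that keeps responders out.

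**2. The planned size.** The plan gives about 50 with no formula, so there is nothing to reproduce exactly. A pool of 56 in the named arms, plus an unstated number from other studies, is the right order of magnitude for a study of failures. It shows how the sponsor itself reads criterion 4.

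**3. How many earlier responders could enter if the Synopsis were ignored.** The documents give no rate of renewed viraemia, so r is assumed. Assume also that viraemic responders enrol as readily as the 56. Their share is 1255r / (1255r + 56).

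- r = 0.1%: 1.26/57.26 = 2.2%, about 1 of 50.
- r = 0.5%: 6.28/62.28 = 10.1%, about 5 of 50.
- r = 1.0%: 12.55/68.55 = 18.3%, about 9 of 50.

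**4. Shift in the SVR12 estimate.** Shift = (k/50) × (rate in earlier responders - rate in the rest). Earlier responders are set at 95.0% to 100%. The rest are set at 97.3% (POLARIS-4), 96.2% (POLARIS-1) or an assumed 90%. These are rough proxies: 95.0% comes from 8 weeks in DAA-naive subjects, and 97.3% from subjects with no earlier NS5A inhibitor. The extremes are:

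- k = 1: 0.02 × (95.0 - 97.3) = -0.05 to 0.02 × (100 - 90) = +0.2 points.
- k = 5: 0.10 × (95.0 - 97.3) = -0.23 to 0.10 × (100 - 90) = +1.0 points.
- k = 9: 0.18 × (95.0 - 97.3) = -0.41 to 0.18 × (100 - 90) = +1.8 points.

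For scale, the Clopper-Pearson 95% interval for 48/50 is 86.3% to 99.5%, about 13 points wide.

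**5. SVR and SVR12.** In the Synopsis and Section 1.3, SVR carries no timepoint, so it does not conflict with SVR12 in Protocol 8.7 and SAP 1.3. The only SVR timepoints that this protocol defines are 4 and 12 weeks, and Protocol 1.2.2 reports the earlier studies' efficacy as SVR12. A subject who reached SVR12 and later became viraemic had achieved SVR at the timepoint by which those studies are reported. Excluding that subject is the natural reading.

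**The case for a change.** The strongest case for a change is that Section 4.2 is the list every subject must satisfy, and the Synopsis itself refers the reader there for detail. Criterion 3 shows viraemia now and says nothing about how the earlier course ended. The sponsor-approval phrase most naturally attaches to the other-study route, so the POLARIS route has no such check, and no condition for approval is written down. One added clause would close the gap. The sponsor ran the earlier studies, so the outcome should be on record.

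The omission stands as a matter of wording. Its consequence does not. The Synopsis is part of the protocol, and its outcome condition sits under the main eligibility heading; a pointer to detailed criteria does not cancel the main ones. The window for renewed viraemia was also short. The SAP dates the protocol to 19 January 2017, and the protocol still describes the three named studies as ongoing, with interim results. Criterion 4 further requires their posttreatment assessments to be complete. Exclusion 19, on recent drug abuse, may remove some reinfections, though it does not touch late relapse.

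The missing subgroup by earlier outcome also carries no weight: in the population that the Synopsis defines, earlier outcome is the same for everyone. Copying the Synopsis wording into criterion 4 would tidy the list, but it would bring the same undated term with it.

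**Conclusion.** No change to the plan is needed. Criterion 4 does not repeat a condition that the Synopsis states three times and that Section 1.3 and the sample-size basis share. Read as a whole, the protocol enrols subjects whose earlier treatment did not produce SVR. This is a drafting gap that sites and analysts fill correctly from the same document.

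No effect on the result can be shown from the documents. The shift of -0.4 to +1.8 points needs three things together: sites disregarding the Synopsis, a renewed-viraemia rate as high as 1.0%, and equal willingness to enrol. The upper end also needs an assumed 90% response in the rest. At 0.1% the shift is at most 0.2 points. SAP 3.5 plans no hypothesis test, so no decision turns on a movement of this size. The conclusion would weaken if sites had screened from Sections 4.2 and 4.3 alone and had enrolled several earlier responders; nothing in the documents suggests that.

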4.3. Exclusion Criteria

Subjects who meet *any* of the following exclusion criteria are not to be enrolled in this study.

- 12) Current or prior history of any of the following:
 - a) Clinically significant illness (other than HCV) or any other major medical disorder that may interfere with subject treatment, assessment or compliance with the protocol; subjects currently under evaluation for a potentially clinically significant illness (other than HCV) are also excluded
 - b) Gastrointestinal disorder or post-operative condition that could interfere with the absorption of the study drug
 - c) Difficulty with blood collection and/or poor venous access for the purposes of phlebotomy
 - d) Hepatic decompensation (e.g., clinical ascites, encephalopathy, and/or variceal hemorrhage)
 - e) Solid organ transplantation
 - f) Significant cardiac disease
 - g) Unstable psychiatric condition including hospitalization, suicide attempt, and/or a period of disability as a result of their psychiatric illness within 2 years prior to Screening

- h) Malignancy within the 5 years prior to Screening, with the exception of specific cancers that have been cured by surgical resection (e.g., basal cell skin cancer, etc.). Subjects under evaluation for possible malignancy are not eligible
 - i) Significant drug allergy (e.g., hepatotoxicity)
- 13) Screening ECG with clinically significant abnormalities
- 14) Subject has the following laboratory parameters at Screening:
- a) $ALT > 10 \times$ the upper limit of normal (ULN)
 - b) $AST > 10 \times$ ULN
 - c) Direct bilirubin $> 1.5 \times$ ULN
 - d) Platelets $< 50,000/\mu\text{L}$
 - e) $HbA1c > 8.5\%$
 - f) Creatinine clearance (Cr_{cl}) < 50 mL/min as calculated by the Cockcroft-Gault equation {Cockcroft 1976}
 - g) Hemoglobin < 10 g/dL
 - h) Albumin < 3 g/dL
 - i) International Normalized Ratio of prothrombin time (INR) $> 1.5 \times$ ULN unless subject has known hemophilia or is stable on an anticoagulant regimen affecting INR
- 15) Prior treatment with SOF/VEL/VOX±RBV for ≥ 12 weeks
- 16) Chronic liver disease of a non-HCV etiology (e.g., hemochromatosis, Wilson's disease, alfa-1 antitrypsin deficiency, cholangitis)
- 17) Infection with human immunodeficiency virus (HIV)
- 18) Hepatitis B surface antigen positive (HBsAg+) at Screening
- 19) Clinically-relevant alcohol or drug abuse within 12 months of Screening. A positive drug screen will exclude subjects unless it can be explained by a prescribed medication; the diagnosis and prescription must be approved by the investigator
- 20) Use of any prohibited concomitant medications as described in Section 5.5
- 21) Known hypersensitivity to the study drug, the metabolites, or formulation excipient

5. INVESTIGATIONAL MEDICINAL PRODUCTS

5.1. Randomization, Blinding and Treatment Codes

This is an open-label study. There will be one treatment group:

- SOF/VEL/VOX FDC (400/100/100 mg) once daily with food for 12 weeks

5.2. Description and Handling of SOF/VEL/VOX FDC Tablets

5.2.1. Formulation

Sofosbuvir/velpatasvir/voxilaprevir (SOF/VEL/VOX) tablets, 400/100/100 mg, are available as beige, capsule-shaped film-coated tablets debossed with “GSI” on one side and a “3” on the other side. In addition to the active ingredients, SOF/VEL/VOX tablets also contain copovidone, microcrystalline cellulose, lactose monohydrate, silicon dioxide, croscarmellose sodium and magnesium stearate. The active tablet film coating material contains polyvinyl alcohol, titanium dioxide, macrogol/polyethylene glycol 3350, talc, iron oxide yellow, iron oxide red, and ferrousferic oxide.

5.2.2. Packaging and Labeling

SOF/VEL/VOX (SOF/VEL/GS-9857) FDC tablets are packaged in white, high density polyethylene (HDPE) bottles. Each bottle contains 28 tablets, silica gel desiccant, and polyester packing material. Each bottle is enclosed with a white, continuous thread, child-resistant screw cap fitted with an induction-sealed, aluminum-faced liner.

SOF/VEL/VOX FDC bottles to be distributed to study centers in the US and other participating countries shall be labeled to meet all applicable requirements of the US Food and Drug Administration (FDA), EU Guideline to Good Manufacturing Practice – Annex 13 (Investigational Medicinal Products) and/or local regulations as applicable.

Sufficient quantities of SOF/VEL/VOX FDC tablets will be shipped to the investigator or qualified designee from Gilead Sciences Clinical Supply Management (or its designee).

5.2.3. Storage and Handling

SOF/VEL/VOX FDC bottles should be stored at controlled room temperature until required for administration. Controlled room temperature is defined as 25°C (77°F); excursions are permitted between 15°C and 30°C (59°F to 86°F).

All drug products should be stored in a securely locked area, accessible only to authorized site personnel. To ensure the stability of the study drug and to ensure proper product identification, the drug product should not be stored in a container other than the container in which they are supplied. Keep the container tightly closed to protect from moisture. Consideration should be

given to handling, preparation, and disposal through measures that minimize drug contact with the body. Appropriate precautions should be followed to avoid direct eye contact or exposure through inhalation when handling SOF/VEL/VOX FDC.

5.3. Dosage and Administration of SOF/VEL/VOX FDC

Subjects will take one tablet of SOF/VEL/VOX FDC once daily with food. For a missed dose of study drug, subjects will be instructed to take the missed dose of study drug as soon as possible during the same day. Subjects will be cautioned never to double the next dose with a missed dose of study drug under any circumstances.

5.4. Study Drug Adherence and Drug Accountability

Subjects must be instructed to bring back all bottles of study drug in the original container at every study visit after Day 1 through the end of treatment.

Study drug will be reconciled using a drug pill count at every study visit after Day 1 by the investigator or designee (i.e. pharmacist), in order to monitor the subject's adherence with the medication regimen.

